8.3 Definitions of analysis sets

The analysis of data will be based on different subsets according to the purpose of the analysis. Throughout the safety results sections, erroneously treated patients (e.g., those assigned to receive dose A, who actually received dose B, those who failed to meet the selection criteria) will be accounted for in the actual dose group received.

Table 15 Analysis sets

Analysis Set	Definition
Safety	All patients who received at least 1 dose of AZD9150, AZD5069, or MEDI4736
Pharmacokinetics	All dosed patients with reportable AZD9150, AZD5069, or MEDI4736 plasma concentrations and no important AEs or protocol deviations that may impact PK
Pharmacodynamics	All patients who provided biological samples for pharmacodynamic research
Efficacy	All patients with unidimensional measurable disease at baseline as per the RECIST 1.1 criteria who received at least 1 dose of study treatment

8.3.1 Efficacy analysis set

All patients with unidimensional measurable disease at baseline as per the RECIST 1.1 criteria who received at least 1 dose of study treatment.

8.3.2 Safety analysis set

All patients who received at least 1 dose of AZD9150, AZD5069, or MEDI4736 tremelimumab (for patients in Arm A4).

8.3.3 PK analysis set

All patients who provided biological samples for pharmacodynamic research.

8.3.4 PD analysis sets

All patients who provided biological samples for pharmacodynamic research.

8.4 Calculation or derivation of safety variables

Safety and tolerability will be assessed in terms of AEs, SAEs, laboratory data, vital signs, ECG changes, and physical examinations. These will be collected for all patients. Appropriate summaries of these data will be presented.

ECG changes

Immediate clinical management of patients will be according to local assessment of the QT interval. For the CSR, QTc will be calculated using Fridericia's formula:

$$QTcF = QT / (\sqrt[3]{RR}).$$

Creatinine clearance

Creatinine clearance may be measured by 24-hour urine collection or calculated by using the Cockcroft and Gault equation (Cockcroft and Gault 1976).

For creatinine values in $\mu\text{mol/L}$:

Men: $[(140-\text{age}) \times \text{weight (kg)} \times 1.23] / \text{serum creatinine } (\mu\text{mol/L})$

Females: $[(140-\text{age}) \times \text{weight (kg)} \times 1.04] / \text{serum creatinine } (\mu\text{mol/L})$

For creatinine values in mg/dL :

Men: $[(140-\text{age}) \times \text{weight (kg)}] / [72 \times \text{serum creatinine (mg/dL)}]$

Females: $0.85 \times [(140-\text{age}) \times \text{weight (kg)}] / [72 \times \text{serum creatinine (mg/dL)}]$

Other significant adverse events

During the evaluation of the AE data, an AstraZeneca medically qualified expert will review the list of AEs. Based on the expert's judgement, AEs of particular clinical importance may, after consultation with the Global Safety Physician, be considered other significant AEs (OAEs) and reported as such in the CSR. A similar review of laboratory values, vital signs, ECGs, and other safety assessments will be performed for identification of OAEs.

8.5 Calculation or derivation of pharmacokinetic variables

Pharmacokinetic analysis of plasma (for all compounds) and urine (for AZD9150 only) concentration data for AZD9150, AZD5069, and MEDI4736 will be performed by a central laboratory on behalf of AstraZeneca. The actual sampling times will be used in the parameter calculations and PK parameters will be derived using standard non-compartmental methods.

Where possible, the following PK parameters will be determined for AZD9150, AZD5069, and MEDI4736.

Pharmacokinetic parameters for AZD9150:

- Single dose: C_{max} , T_{max} , $AUC_{(0-\infty)}$, $AUC_{(0-t)}$, $AUC_{(0-48)}$, CL , V_z/F , MRT , $t_{1/2}$, as data permit
- Multiple dose: $C_{\text{ss max}}$, $C_{\text{ss min}}$, $T_{\text{ss max}}$, C_{trough} , $AUC_{(0-24)}$, V_{ss} , extent of accumulation on multiple dosing (R_{ac}), A_e , and $\%F_e$

Pharmacokinetic parameters for AZD5069:

- Single dose: C_{max} , T_{max} , $AUC_{(0-\infty)}$, $AUC_{(0-t)}$, $AUC_{(0-24)}$, apparent plasma clearance (CL/F), apparent volume of distribution (V_d/F), MRT , and $t_{1/2}$, as data permit

- Multiple dose: $C_{ss\ max}$, $T_{ss\ max}$, C_{trough} , $AUC_{(0-24)}$, V_{ss}/F , apparent plasma clearance at steady state (CL_{ss}/F), R_{ac}

Pharmacokinetic parameters for MEDI4736:

- C_{max} , T_{max} , C_{trough}

8.6 Calculation or derivation of pharmacodynamic variables

Change from baseline and percent change from baseline for pharmacodynamic variables will be calculated for all patients.

8.7 Pharmacokinetics/Pharmacodynamic analysis

The plasma concentration data for AZD9150, MEDI4736, tremelimumab, and AZD5069 may be analysed using a population PK approach, which may include exploring the influence of covariates on PK, if the data allows. A population pharmacodynamic approach will be used to investigate the relationship between PK and selected primary, secondary, and/or exploratory endpoints, where deemed appropriate. Results may be reported separately from the CSR for the main study. The PK, pharmacodynamic, demographic, safety, and tumor response data collected in this study may also be combined with similar data from other studies and explored using population PK and/or PK-pharmacodynamic methods. The results of any such analyses will be reported separately from the CSR.

8.8 Calculation or derivation of exploratory research variables

Results from the exploratory biomarker research and/or pharmacogenetic research will be reported separately from the CSR for the main study.

8.9 Calculation or derivation of tumor response variables

At each visit, patients will be programmatically assigned a RECIST version 1.1 overall visit response of CR, PR, SD, or PD, not evaluable (NE) depending on the status of their disease compared with baseline and previous visit assessments.

Progression of TLs will be calculated in comparison to when the tumor burden was at a minimum (i.e., smallest sum of diameters previously recorded on study, including baseline). In the absence of progression, tumor response (CR, PR, and SD) will be calculated in comparison to the baseline tumor measurements obtained before starting treatment.

If a patient has had a tumor assessment that cannot be evaluated (either because the scan was unreadable or taken before Day 15 of Cycle 2), the patient will be assigned an overall visit response of NE unless there is evidence of progression, in which case the response will be assigned as PD.

For TL measurements, if one-third of the TL sizes are missing then a scaling up rule will be applied as follows:

- If \leq one-third of all lesions recorded at baseline are missing, the results will be scaled up (based on the nadir sizes, including baseline) to give an estimated sum of diameters and this will be used in calculations. (This is equivalent to comparing the visit sum of diameters of the non-missing lesions to the nadir sum of diameters excluding the lesions that are missing and determining at what rate the lesions are changing.)
- If $>$ one-third of all lesions recorded at baseline are missing, the TL response will be NE. However, if the sum of non-missing TL diameters would result in PD (i.e., if using a value of 0 for missing lesions the sum of diameters has still increased by $>20\%$ or more compared with the smallest sum of diameters on study); PD takes precedence over NE.
- Only responses of PR, SD, PD, or NE will be permitted if any of the TL data are missing.

An overall visit response of CR is defined when all TL and NTL lesions present at baseline have disappeared (with the exception of lymph nodes, which must be less than 10 mm to be considered non-pathological) and no new lesions have developed since baseline. An overall visit response of PR is defined when the sum of diameters of the TLs has decreased by 30% or more compared with baseline (with no evidence of progression) and the NTLs are at least stable with no evidence of new lesions. To be assigned a status of PR or CR, changes in tumor measurements must be confirmed by repeat assessments that should be performed no less than 4 weeks after the criteria for response are first met.

SD is defined as neither sufficient shrinkage to qualify for PR nor sufficient increase to qualify for PD. In the case of SD, follow-up measurements must have met the SD criteria at least once after study entry at a minimum interval of not less than 35 days.

When the Investigator is in doubt as to whether PD has occurred and therefore reassesses the patient at a later date, the date of the initial scan should be declared as the date of progression if the repeat scans confirm progression.

Best overall response

A best overall response (CR, PR, SD, PD, or NE ordered from best to worst here) will be determined for each patient based on the best overall visit response recorded from start of study treatment to the EOT, including any assessments for confirmation after the EOT. Confirmation (values of CR or PR in the case of PR and CR for CR is required for best overall response values of CR or PR).

Objective response

A patient is said to have an objective response if he/she has had at least 1 response of confirmed CR or PR before any evidence of progression (as defined by RECIST version 1.1) that is confirmed at least 4 weeks later.

Disease control

A patient is said to have achieved disease control at a given visit if they have a tumor response of SD, PR, or CR at that visit. Disease control will be assessed at 12 weeks after the start of study drug and is defined as the proportion of all patients dosed that have an overall visit response of SD, PR, or CR at Week 12. Therefore, earlier overall visit responses of CR or PR that become PD at Week 12 or NE responses at Week 12 do not constitute disease control at 12 weeks. A time window of 1 week around the Week 12 visit will be applied, and it is recommended that any visits occurring 11 weeks or more after dosing are acceptable; however, if an earlier visit is defined as PD, the overall visit response at Week 12 would also be defined as PD. If the Week 12 overall response is missing or NE but the next evaluable response is SD or better, the patient will be defined as having an overall visit response of SD, PR, or CR at 12 weeks.

Duration of response

Duration of response will be defined as the time from the date of first documented confirmed response until date of documented progression or death in the absence of disease progression. The end of response should coincide with the date of progression or death from any cause used for the PFS endpoint. The time of the initial response will be defined as the latest of the dates contributing towards the first overall visit response of PR or CR.

If a patient does not progress following a response, then his/her DOR will use the PFS censoring time.

Durable response

A patient is said to have a durable response of 3 months if they have either a confirmed CR or PR that lasts 3 months following the initial confirmation of the response.

Progression-free survival

Progression-free survival is defined as the time from start of treatment (Cycle 1, Day 1) until the date of objective disease progression or death (by any cause in the absence of progression) regardless of whether the patient withdraws from therapy or receives another anticancer therapy before progression. Patients who have not progressed or died at the time of analysis will be censored at the time of the latest date of assessment from their last evaluable RECIST version 1.1 assessment. However, if the patient progresses or dies after 2 or more missed visits, the patient will be censored at the time of the latest evaluable RECIST version 1.1 assessment. If the patient has no evaluable visits or does not have baseline data, he/she will be censored at 0 days unless he or she dies within 2 visits of baseline.

The PFS time will always be derived based on scan/assessment dates not visit dates.

RECIST version 1.1 assessments/scans contributing towards a particular visit may be performed on different dates. The following rules will be applied:

- Date of progression will be determined based on the earliest of the dates of the component that triggered the progression
- When censoring a patient for PFS the patient will be censored at the latest of the dates contributing to a particular overall visit assessment

Overall survival

Overall survival is defined as the time from the date of Cycle 1, Day 1 until death due to any cause. Any patient not known to have died at the time of analysis will be censored based on the last recorded date on which the patient was known to be alive.

Survival at 12 months

Patients who are alive 1 year following the beginning of treatment are said to have survived 12 months. Patients whose vital status is unknown at 12 months will be censored at the last date that the patient was known to be alive.

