For Arm A6: the dose and safety confirmation cohort AZD9150 will be given in combination with MEDI4736 at established doses of AZD9150 (from Arms A1, A2/A3) in combination with a fixed dose of MEDI4736. This will be done in patients with prostate cancer and there will be no intra-patient dose escalation. If the dose is not tolerated in this combination of 2 drugs, then dose-reduction will be conducted as shown in [Figure 4](#), [Figure 7](#), and [Figure 8](#).

Potential subjects who provide written informed consent will be screened; those who are identified as eligible will be enrolled, assessed by the Investigator for treatment with AZD5069, and assigned accordingly to a treatment arm. Following a 7-day lead-in period during which only AZD9150 or AZD5069 will be administered, combination treatment with MEDI4736 and/or tremelimumab starts on Day 1 of Cycle 1. A cycle of study treatment is defined as 28 days.

Each patient will undergo assessments for safety (DLTs, AEs, vital sign measurements, clinical laboratory tests, PS, ECGs, and physical examinations) and other assessments according to the study plan (see [Section 5.2](#)).

The DLT evaluation period will be defined as the time from the first dose of AZD9150 or AZD5069 to the end of Cycle 1 (i.e., 35 days total), or until a patient experiences a DLT, whichever occurs first. For patients in treatment arm A4 (AZD9150/MEDI4736/tremelimumab), to be deemed evaluable, a patient must have received all 3 loading doses of AZD9150 during the 7-day lead-in period, and at least 3 additional doses during Cycle 1, as well as the MEDI4736 and tremelimumab infusion during the DLT evaluation period. Patients who have suffered a DLT during or before Day 35 will also be deemed evaluable. For patients in treatment arm A3 (AZD5069/MEDI4736) to be deemed evaluable, they must have received all doses during the 7-day lead-in period (i.e., 14 doses) and at least 50% of the planned doses of AZD5069.

For Arm A6, the aim is to establish, collect, and confirm safety, tolerability, and PK/pharmacodynamic relations of the RP2D/MT2D for the 2 combinations (i.e., AZD9150/MEDI4736 and AZD5069/MEDI4736) in specific tumor types of prostate cancer at established doses from Arms A1, A2, and A3. Hence, Arm A6 will not be followed for DLTs.

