- j For women of childbearing potential, defined as those who are not surgically sterile (i.e., bilateral tubal ligation, bilateral oophorectomy, or complete hysterectomy) or postmenopausal (defined as 12 months with no menses without an alternative medical cause): A blood sample to determine serum β hCG is required at screening; this sample will be analysed at the central laboratory for the study. Additionally, urine samples for a urine-based pregnancy test will be collected before dosing on Day -7 of the lead-in, before dosing on Day 1 of each cycle, and at the EOT visit. Urine-based pregnancy tests will be performed at the study centres.
- k Tumor assessments to be performed at screening, on Day 15 of Cycle 2 (i.e., at the beginning of Week 7), at the beginning of each subsequent even-numbered cycle, and at the EOT visit. Patients who are on study treatment for more than 24 months may have the frequency of tumor assessment reduced to every 12 to 16 weeks at the discretion of the Investigator. Patients who discontinue treatment for reasons other than PD will continue to undergo tumor assessments every 2 months (\pm 7 days) until PD is noted. To facilitate scheduling of tumor assessments, a window of \pm 7 days is allowed. For the additional 48 patients to be enrolled in first-line in Arms B7 and B8, a central imaging read will be done in addition to the local site RECIST evaluation. See Section 5.3.1 for additional details.

- ^l The reporting period for AEs and concomitant medication starts immediately following the time that written informed consent is obtained and ends 28 (+7) days after the last dose of study drug or until the initiation of subsequent anticancer therapy. For patients dose-reduced to levels -1 or -2 of AZD9150 in Arms B1, B3, or B7 who are experiencing treatment-related AEs of Grade 2 or lower, visits on Day 8 and Day 22 of each cycle (no AZD9150 dosing) may be considered optional, unless, in the Investigator's estimation, more frequent individual evaluations are appropriate.

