5.3 Efficacy assessments

5.3.1 Tumor assessments

Tumor assessments will be performed at screening, on Day 15 of Cycle 2, at the beginning of Week 7, at the beginning of each subsequent even-numbered cycle, and at the EOT visit. Patients who are on study treatment for more than 24 months may have the frequency of tumor assessment reduced to every 12 to 16 weeks at the discretion of the Investigator. Patients who discontinue treatment for reasons other than PD will continue to undergo tumor assessments every 2 months (± 7 days) until PD is noted.

It is important to follow the assessment schedule as closely as possible. To facilitate scheduling of tumor assessments, a window of ± 7 days is allowed.

Baseline tumor assessments should encompass all areas of known predilection for metastases in the disease under evaluation and should additionally investigate areas that may be involved based on signs and symptoms of individual patients. Baseline assessments should be performed no more than 21 days before the start of study treatment and ideally should be performed as close as possible to the start of study treatment. Tumor assessments obtained as standard of care before consent may be used for the study provided the assessments fall within the protocol-specified period before the first dose of study treatment.

Tumor assessments may include the following evaluations: Physical examination (with photograph and measurement of skin lesions as applicable); CT or MRI scan of the chest, abdomen, and pelvis; and CT or MRI scan of the brain. CT or MRI scan of the brain will be performed only at screening or if the patient is neurologically symptomatic. The preferred method of disease assessment is CT with contrast. If CT with contrast is contraindicated, CT without contrast is preferred over MRI. The methods of assessment used at baseline should be used at each subsequent follow-up assessment. Any other sites at which new disease is suspected should also be appropriately imaged. If an unscheduled assessment is performed and the patient has not progressed, every attempt should be made to perform subsequent assessments at the scheduled visits while the patient remains on study treatment.

Sites will be required to store electronic copies of all scans, and the study Sponsor may arrange for possible centralized storage of all imaging data. The centralized storage of imaging data would be for possible independent centralized review of disease assessments.

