## Statistical Analysis Plan

be confirmed at least 4 weeks after the initial assessment of PD. The modified RECIST guidelines version 1.1 for measurable, non-measurable, target lesions (TLs), non-target lesions (NLTs) and the objective tumour response criteria are presented in Appendix F of the clinical study protocol. These criteria will also be used to determine if and when a patient has progressed in accordance with RECIST and to determine their best objective response.

Baseline radiological tumour assessments are to be performed no more than 28 days before the start of study treatment and should ideally be performed as close as possible to the start of study treatment. Tumour assessments are then performed on Day 15 of Cycle 2 (i.e., at the start of Week 7), at the beginning of each subsequent even-numbered cycle, and at the End of Treatment (EOT) visit. Patients who discontinue treatment for reasons other than PD will continue to undergo tumour assessments every 2 months until PD is noted. To facilitate tumour assessments, a window of  $\pm 3$  days is allowed.

The number and percentage of patients who fell into each of the overall tumour response categories (CR, PR, SD, PD, or NE), into each of the response categories for TLs (CR, PR, SD, PD, or NE), and into the response categories for NLTs (CR, Non-CR/Non PD, PD, NE) will be summarized by treatment group and visit. All tumour response data will be listed.

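### Protocol 8.9 sets a CR, PR or SD seen before Cycle 2 Day 15 to not evaluable, although the permitted first-scan window opens at Cycle 2 Day 8; the SAP neither repeats nor revokes the rule

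*Protocol*

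**What the plan says.** **The rule.** Protocol 8.9 names two reasons why an assessment cannot be evaluated: "either because the scan was unreadable or taken before Day 15 of Cycle 2". Such a visit is "assigned an overall visit response of NE unless there is evidence of progression, in which case the response will be assigned as PD". No exception is made for a scan inside its visit window.

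**The schedule.** Protocol Table 5 note k places the first on-treatment scan "on Day 15 of Cycle 2 (i.e., at the beginning of Week 7"). Protocol 5.3.1 gives the same day and continues: "To facilitate scheduling of tumor assessments, a window of" ± 7 days. Appendix F 4.1 states 6 weeks ± 1 week.

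**Stable disease.** Later in protocol 8.9, SD must have been met at least once after study entry "at a minimum interval of not less than 35 days". SAP 8.3.2 also uses 35 days.

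**The SAP.** SAP 8.1 repeats the schedule ("Tumour assessments are then performed on Day 15 of Cycle 2") but gives a different tolerance: "To facilitate tumour assessments, a window of" ± 3 days, as does SAP 6.2. SAP 8.2.2 takes the primary variable from SAP 8.1, which refers to Appendix F for the response criteria. None of these carries the Day 15 cut-off. SAP Section 13 lists no change on this point.

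**The concern.** A cut-off for a scan that is too early would normally sit at the lower edge of the visit window. Here it sits on the nominal day. A site that follows the protocol and scans a few days early has its CR, PR or SD turned into NE.

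Confirmed ORR is the Part B primary endpoint. The rule removes response readings and adds none, so its effect on ORR goes one way. Other endpoints follow:

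- The start of DOR and the time to first response move to a later scan.
- If the early scan is the only one, SD or an unconfirmed PR becomes NE, and the patient has no evaluable visit. PFS is then censored at day 0, unless the patient dies within two visits of baseline (protocol 8.9, SAP 8.3.7).
- If that patient dies within 18 weeks of first dose, SAP 8.3.2 assigns a best response of PD.

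Because the SAP is silent, two programmers could derive different ORRs from the same data, each with support in the documents.

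**Working it through.** **Calendar.** Protocol 4.1.2: "A cycle of study treatment is defined as 28 days". Counting Cycle 1 Day 1 as Day 1:

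- Cycle 2 Day 15 = 28 + 15 = Day 43. (43 − 1)/7 = 6 completed weeks, so Day 43 is the first day of Week 7. This reproduces the protocol's own statement.
- Cycle 4 Day 1 = 3 × 28 + 1 = Day 85. Cycle 6 Day 1 = 5 × 28 + 1 = Day 141.

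**Permitted days caught by the cut-off**

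| Window | Permitted days | In Cycle 2 | Before Day 43 | Share |
|---|---|---|---|---|
| Protocol, ± 7 days | 36–50 | Days 8–22 | 36–42 | 7/15 = 47% |
| SAP, ± 3 days | 40–46 | Days 12–18 | 40–42 | 3/7 = 43% |

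These are shares of permitted days. They are not shares of patients.

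**One patient, two scan days.** Suppose PR at the first scan, PR at Cycle 4 Day 1 and PD at Cycle 6 Day 1.

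- First scan on Cycle 2 Day 15 (Day 43): the two PRs are 85 − 43 = 42 days apart, more than 4 weeks. Responder.
- First scan on Cycle 2 Day 12 (Day 40): the gap is 85 − 40 = 45 days, also more than 4 weeks. Under protocol 8.9, however, the sequence reads NE, PR, PD. The PR is unconfirmed, and the patient is a non-responder.

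After an NE first scan, a PR at Day 85 needs another PR. The next scheduled scan is 141 − 85 = 56 days later.

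**Size, as an illustration only.** The documents give no distribution of scan days, no share of responses present at week 7 and no DOR. All three are assumptions here:

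- e = share of first scans taken early within the window: 10%, 25%, or 47% (scan days spread evenly over the 15 days).
- 80% of responses already present at week 7.
- Exponential DOR with a median of m = 3, 6 or 12 months of 30.4 days.
- d = extra days the response must last: 28 (the minimum for confirmation) or 56 (the next scheduled scan).

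Loss = 1 − exp(−ln 2 × d/(30.4 × m)). Measured ORR = 25% × (1 − e × 0.8 × loss).

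- d = 56: loss = 0.347, 0.192, 0.101 for m = 3, 6, 12.
- d = 28, m = 12: loss = 0.052.
- e = 7/15, d = 56: measured ORR = 21.8%, 23.2%, 24.1%.
- e = 25%, d = 56, m = 3: 23.3%. e = 10%, d = 28, m = 12: 24.9%.

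A second illustration uses a true ORR of 35%. If 10% to 47% of first scans are early and 10% to 30% of responders need that scan for confirmation:

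- Smallest loss: 35% × (1 − 0.10 × 0.10) = 34.7%.
- Largest loss: 35% × (1 − 0.467 × 0.30) = 30.1%.
- The binomial chance of at least 13 responses in 48 falls from 90.6% to 89.7% and 72.5% respectively.

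For scale, the planned exact 80% interval for 12/48 runs from 16.9% to 34.8%.

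**The case against.** **It is not shown that the analysis applies the rule.** Protocol 8.1 defers to the SAP for detail. The SAP derives response from Appendix F, where NE depends on lesions that were not assessed, could not be evaluated or had an intervention. This stands in part: it cannot be said that responses are being discarded. But the SAP does not list the omission as a change, so the protocol rule remains in force on paper and the derivation is undetermined.

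**Letting early PD count is deliberate.** A reader might infer that the different treatment of PD is itself a fault and that the cut-off should apply to PD too. The documents do not support that. Protocol 8.9 and Appendix F let PD override NE throughout, and extending the cut-off would turn real early progression into NE. Nor does an early PD reading always settle the matter: without clinical deterioration it must be confirmed at least 4 weeks later (protocol 5.3.1.1, SAP 8.1).

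**The 35-day SD interval does not prove the point.** From Cycle 1 Day 1, 35 days is Day 36, the lower edge of the 7-day window. But study entry is not defined. From the first lead-in dose on Day −7 it is Cycle 2 Day 1. A minimum interval for SD is also compatible with a later limit on evaluability. The conflict rests on the visit window and Appendix F 4.1.

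**The effect is probably modest.** Protocol 5.3.1 asks sites to keep closely to the schedule, so an even spread of scan days is an upper-end assumption. Later scheduled, unscheduled or EOT scans will still confirm many responders. ORR is descriptive, and the illustrated losses are small beside the 80% interval. All of this stands.

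**The stopping rules are past.** Part B enrolment is closed, so no recruitment decision can now change. This stands.

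**Changing the rule now has a cost.** The trial is open-label, the protocol already reports interim response data (Section 1.2), and relaxing the cut-off can only raise ORR or leave it unchanged. This stands and shapes the fix.

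**Conclusion.** The conflict is real and bears on how the primary endpoint is derived. Protocol 8.9 scores a compliant CR, PR or SD on Cycle 2 Days 8 to 14 as NE. Protocol 5.3.1, Table 5 note k and Appendix F 4.1 treat those days as acceptable, and the SAP does not resolve it. If applied, the rule can only lower confirmed ORR or leave it unchanged. It can delay response dates, and it can leave a patient with a single early scan without an evaluable visit.

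The size cannot be stated from the documents. Under the assumptions shown, a true ORR of 25% would be measured as 21.8% to 24.9%, with the low end needing evenly spread scan days, a short DOR and no scan before Cycle 6. A reader might infer that nearly half of first-scan responses are lost. That does not follow: 47% counts permitted days, and a patient loses responder status only if the early scan was needed for the confirmed pair.

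**What to change.** 1. In protocol 8.9 and SAP 8.1, set the NE cut-off at the lower limit of the permitted first-scan window: Cycle 2 Day 8 under the protocol's 7-day window. If the SAP's 3-day window were adopted instead, it would be Cycle 2 Day 12.
2. Keep the rule that PD overrides NE.
3. State one scan window in protocol 5.3.1, Appendix F 4.1 and SAP 6.2 and 8.1.
4. Record the change in SAP Section 13 before the response program is run.
5. Because the change can only raise ORR or leave it unchanged in an open-label trial, report how many patients in each arm have a different response status under the Day 15 cut-off.

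The cost is a few sentences in the two documents, one changed condition in the visit-response program and one extra count per arm. No new data are needed.
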